11. MANAGEMENT AND REPORTING OF ADVERSE EVENTS/ADVERSE REACTIONS

Procedures for the collection, management and reporting of individual cases of adverse events/adverse reactions (see [001-MCS-05-501-RD-01](#) for collection requirements) and of any new information that might influence the evaluation of the benefit-risk balance of the product while the study is being conducted.

11.1 DEFINITIONS OF ADVERSE EVENTS

Adverse event

An AE is defined as any untoward medical occurrence in a patient or clinical investigation subject administered a medicinal product and which does not necessarily have a causal relationship with this treatment. An AE can therefore be any unfavourable and unintended sign (e.g. an abnormal laboratory finding), symptom, or disease temporally associated with the use of a medicinal product, whether or not considered related to the medicinal product.

Adverse reaction

An adverse reaction is defined as a response to a medicinal product which is noxious and unintended. Response in this context means that a causal relationship between a medicinal product and an AE is at least a reasonable possibility. Adverse reactions may arise from use of the product within or outside the terms of the marketing authorisation or from occupational exposure. Conditions of use outside the marketing authorization include off label use, overdose, misuse, abuse and medication errors.

Serious adverse event

A SAE is defined as any AE which

- results in death,
- is life-threatening,
- requires in-patient hospitalization, or
- prolongation of existing hospitalisation,
- results in persistent or significant disability or incapacity, or
- is a congenital anomaly/birth defect

Life-threatening in this context refers to a reaction in which the patient was at risk of death at the time of the reaction; it does not refer to a reaction that hypothetically might have caused death if more severe.

Medical and scientific judgement should be exercised in deciding whether other situations should be considered serious reactions, such as important medical events that might not be immediately life threatening or result in death or hospitalisation but might jeopardise the patient or might require intervention to prevent one of the other outcomes listed above. Examples of such events are intensive treatment in an emergency room or at home for allergic bronchospasm, blood dyscrasias or convulsions that do not result in hospitalisation or development of dependency or abuse. Any suspected transmission via a medicinal product of an infectious agent is also considered a serious adverse reaction.

An AE which possibly leads to disability will be reported as an SAE. Every new occurrence of cancer or an exacerbation of an existing cancer will be reported as a SAE regardless of the duration between discontinuation of the drug and the occurrence of the cancer.

No AESIs have been defined for this study.

11.2 ADVERSE EVENT AND SERIOUS ADVERSE EVENT REPORTING

The investigator shall maintain and keep detailed records of all AEs in their patient files.

Collection of AEs

The study design is of non-interventional nature and the study is conducted within the conditions of the approved marketing authorization. Sufficient data from controlled interventional trials are available to support the evidence on the safety and efficacy of the studied BI drug. For this reason the following AE collection and reporting requirements have been defined.

The following must be collected by the investigator in the eCRF. When any adverse events occur, the data should be immediately entered into eCRF and transmitted. :

- all ADRs (serious and non-serious),
- all AEs with fatal outcome,

All ADRs, including those persisting after study completion must be followed up until they are resolved, have been sufficiently characterized, or no further information can be obtained.

The investigator carefully assesses whether an AE constitutes an ADR using the information below.

Causal relationship of adverse event

The definition of an adverse reaction implies at least a reasonable possibility of a causal relationship between a suspected medicinal product and an AE. An adverse reaction, in contrast to an AE, is characterized by the fact that a causal relationship between a medicinal product and an occurrence is suspected.

Medical judgment should be used to determine the relationship, considering all relevant factors, including pattern of reaction, temporal relationship, de-challenge or re-challenge, confounding factors such as concomitant medication, concomitant diseases and relevant history.

Arguments that may suggest a **reasonable causal relationship** could be:

- The event is **consistent with the known pharmacology** of the drug
- The event is known to be caused by or **attributed to the drug class**.
- **A plausible time to onset of the event** relative to the time of drug exposure.
- Evidence that the **event is reproducible** when the drug is re-introduced
- **No medically sound alternative etiologies** that could explain the event (e.g. preexisting or concomitant diseases, or co-medications).

- The event is typically **drug-related and infrequent in the general population** not exposed to drugs (e.g. Stevens-Johnson syndrome).
- An indication of dose-response (i.e. greater effect size if the dose is increased, smaller effect size if dose is diminished).

Arguments that may suggest that there is **no reasonable possibility of a causal relationship** could be:

- No plausible time to onset of the event relative to the time of drug exposure is evident (e.g. pre-treatment cases, diagnosis of cancer or chronic disease within days/weeks of drug administration; an allergic reaction weeks after discontinuation of the drug concerned)
- Continuation of the event despite the withdrawal of the medication, taking into account the pharmacological properties of the compound (e.g. after 5 half-lives). Of note, this criterion may not be applicable to events whose time course is prolonged despite removing the original trigger.
- Additional arguments amongst those stated before, like alternative explanation (e.g. situations where other drugs or underlying diseases appear to provide a more likely explanation for the observed event than the drug concerned).
- Disappearance of the event even though the study drug treatment continues or remains unchanged.

Intensity of adverse event

The intensity of the AE should be judged based on the following:

Mild: Awareness of sign(s) or symptom(s) which is/are easily tolerated

Moderate: Enough discomfort to cause interference with usual activity

Severe: Incapacitating or causing inability to work or to perform usual activities

Pregnancy:

In rare cases, pregnancy might occur in a study. Once a subject has been enrolled into the study, after having taken TRADIANCE® Combination Tablets AP or BP, the investigator must report any drug exposure during pregnancy, which occurred in a female subject or in a partner to a male subject to the Sponsor by means of Part A of the Pregnancy Monitoring Form. The outcome of the pregnancy associated with the drug exposure during pregnancy must be followed up and reported by means of Part B of the Pregnancy Monitoring Form.

In the absence of a reportable AE, only the Pregnancy Monitoring Form must be completed, otherwise the Non-interventional Study AE form is to be completed and forwarded as well as soon as possible.

Priority survey items:

Fluid volume decreased events and Hypoglycaemia (important identified risks), safety of administration to patients with renal impairment or elderly patients (important missing information) stated in the Japan Risk Management Plan

Information required

For each reportable adverse event, the investigator should provide the information requested on the appropriate (e)CRF pages.

Reporting of related Adverse Events associated with any other BI drug

The investigator is encouraged to report all AEs related to any BI drug other than TRADIANCE® Combination Tablets AP and BP, according to the local regulatory requirements for spontaneous AE reporting at the investigator's discretion by using the locally established routes and AE report forms. The term AE includes drug exposure during pregnancy, and, regardless of whether an AE occurred or not, any abuse, off-label use, misuse, medication error, occupational exposure, lack of effect, and unexpected benefit.

11.3 REPORTING TO HEALTH AUTHORITIES

Adverse event reporting to regulatory agencies will be done by the MAH according to the local and international regulatory requirements.

12. PLANS FOR DISSEMINATING AND COMMUNICATING STUDY RESULTS

The progress reports and final reports will be submitted to PMDA in Japan Periodic safety report. And also the final report for this PMS is included in re-examination documents.

This study is planned for the publication based on the final report.

The rights of the physician and of the sponsor with regard to publication of the results of this PMS study are described in the contract. As a general rule, no PMS study results should be published prior to finalization of the Study Report.

In addition, further interim analysis might be performed for the scientific presentations and publications for the purposes of promoting appropriate use of TRADIANCE® Combination Tablets AP and BP.

ANNEX 1. LIST OF STAND-ALONE DOCUMENTS

Number	Document Reference Number	Date	Title
None	None		

ANNEX 2. FLOW CHART OF VARIABLES

Item	Time point Before first administration of TRADIANCE® Combination Tablets AP or BP	Observation period ^{*1}			
		Week 12	Week 26	Week 40	Week 52 or at discontinuation
Registration	X ^{*2}				
Demographics	X				
Physical examination (Body weight, height)	X	X ^{*3}	X ^{*3}	X ^{*3}	X ^{*3}
HbA1c and fasting plasma glucose	X	X	X	X	X
Concomitant disease/ medical history	X				
Waist circumference	X				
Prior Antidiabetic drugs	X ^{*4}				
Administration status of TRADIANCE® Combination Tablets AP or BP		X (Record throughout the observation period)			
Concomitant drug and Concomitant therapy	X*	X (Record throughout the observation period)			
Blood pressure, pulse rate and ECG	(X)	(X)	(X)	(X)	(X)
Pregnancy status ^{*5}	X (confirm throughout the observation period)		X (confirm throughout the observation period)		
Laboratory tests	(X)	(X)	(X)	(X)	(X)
Adverse events		X (Examine throughout the observation period)			

*1: Time points during the observation period are approximate. Collected data should be reported as of the closest available visit.

*2: Patients administered TRADIANCE® Combination Tablets AP or BP will be registered within 14 days from whenever the day of first administration is possible.

*3: Body weight only

*4: From 3 month before first administration of TRADIANCE® Combination Tablets AP or BP

*5: Only for female patients

(X): If applicable

eCRF (electronic case report form): At 26 weeks, 52 weeks, and each time an adverse event has occurred, data in corresponding observation period should be entered into the eCRF and transmitted using the EDC system.

APPROVAL / SIGNATURE PAGE

[figure not shown]
[figure not shown]
[figure not shown]
[figure not shown]
[figure not shown]
[figure not shown]
[figure not shown]
[figure not shown]
Document Number: c20025178

Technical Version Number: 2.0

Document Name: 1275-0026-nis-protocol-revision-01

Title: Post Marketing Surveillance in Japan on Long Term Drug Use of TRADIANCE Combination Tablets AP and BP in Patients with type 2 Diabetes Mellitus

Signatures (obtained electronically)

Meaning of Signature	Signed by	Date Signed
Author-Clinical Trial Leader		23 Nov 2018 08:10 CET
Approval-EU Qualified Person Pharmacovigilance		23 Nov 2018 08:37 CET
Approval-Team Member Medical Affairs		23 Nov 2018 09:26 CET
Approval-Therapeutic Area		23 Nov 2018 09:51 CET
Approval-  Pharmacovigilance		23 Nov 2018 11:10 CET
Approval-Team Member Drug Safety		23 Nov 2018 11:15 CET

## **2. LIST OF ABBREVIATIONS**

Include a list of all abbreviations used in the TSAP

Term	Definition / description
ADR	Adverse Drug Reaction
ADS	Analysis Data Set
AE	Adverse Event
BICMQ	Boehringer Ingelheim Customised MedDRA Query
BMI	Body Mass Index
CRF	Case Report Form
DPP-IV	Dipeptidyl Peptidase-IV
ECG	Electrocardiogram
eGFR	Estimated Glomerular Filtration Rate
EMA	European Medicines Agency
EOT	End-of-Treatment
FPG	Fasting Plasma Glucose
GLP-1	Glucagon-Like Peptide-1
HbA1c	Glycosylated haemoglobin
MedDRA	Medical Dictionary for Regulatory Activities
NIS	Non-interventional Study
NYHA	New York Heart Association Functional Classification
PMS	Post-Marketing Surveillance
PT	Preferred Term
PV	Protocol Violation
Q1	Lower quartile
Q3	Upper quartile
SADR	Serious Adverse Drug Reaction
SAE	Serious Adverse Event
SD	Standard deviation
SGLT2	Sodium Glucose cotransporter 2
SMQ	Standardised MedDRA query
SOC	System organ class

Term	Definition / description
TSAP	Trial Statistical Analysis Plan

### **3. INTRODUCTION**

The purpose of this document is to provide a more technical and detailed elaboration of the principal features of the analysis described in the protocol, and to include detailed procedures for executing the statistical analysis of the post-marketing surveillance (PMS) data.

This TSAP assumes familiarity with the Non-interventional Study Protocol (NIS Protocol), including Protocol Amendments. In particular, the TSAP is based on the planned analysis specification as written in NIS Protocol Section 9.7 “DATA ANALYSIS”. Therefore, TSAP readers may consult the NIS Protocol for more background information on the study, e.g., on study objectives, study design and population, treatments, definition of measurements and variables, planning of sample size.

SAS® Version 9.4 or later will be used for all analyses.

**4. CHANGES IN THE PLANNED ANALYSIS OF THE STUDY**

No change has been made in the planned analyses from the statistical methods described in the NIS Protocol.

**5. ENDPOINT(S)**

**5.1 PRIMARY ENDPOINT(S)**

Incidences of adverse drug reactions (ADRs)

[figure not shown]
**5.2 SECONDARY ENDPOINT(S)**

[figure not shown]
**5.2.1 Key secondary endpoint(s)**

[figure not shown]
This section is not applicable as no key secondary endpoint has been specified in the protocol.

**5.2.2 Secondary endpoint(s)**

None

## **6. GENERAL ANALYSIS DEFINITIONS**

### **6.1 TREATMENT(S)**

For basic study information on treatments, please refer to NIS Protocol Section 4. The technical specification for treatment set-up is described in the analysis data set (ADS) plan.

For effectiveness analyses, data up to 7 days after last treatment intake will be considered as on treatment for HbA1c and 1 day for FPG. For safety analyses, data up to 7 days after last treatment intake will be considered as on treatment for AE, 1 day for weight, blood pressure and pulse and 3 days for laboratory measurements.

### **6.2 IMPORTANT PROTOCOL VIOLATIONS**

The following [table 6.2:1](#) defines the different categories of important PVs. The final column describes which PVs will be used to exclude patients from each patient analysis sets.

Observed PVs will be concluded as important or not important at report planning meetings before database lock at the latest.

[figure not shown]
Table 6.2:1 Important protocol violations

[figure not shown]
Category/ Code		Description	Example/Comment	Method	Excluded from
A		Entrance criteria not met			
A1.1		No type 2 diabetes		Automated	Effectiveness
A1.2		Patient received TRADIANCE® treatment before registration		Automated	All
B		Informed consent			
C		Trial medication and randomization			
C1		Incorrect trial medication taken			
C1.1		No treatment with TRADIANCE®		Automated	All
E		Missing data			
E1		No values of both HbA1c and FPG at both baseline and visit except for baseline	No available values of both HbA1c and FPG at both baseline and visit except for baseline	Automated	Effectiveness
G		Trial specific			
G1		Invalid registration			
G1.1		No patient visit after entry	Patient made no visit after the entry	Automated	All
G1.2		Multiple registration	Patient who were already registered in this trial with another patient ID In this case, all data for the later patient will not be used.	Manual	All
G1.3		Registration rule not followed		Manual	All
G1.4		Patient started TRADIANCE® treatment out of registration period		Manual	All
G1.5		Not continuous investigation		Manual	All

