9.2.2.1 Inclusion/ exclusion criteria

Inclusion criteria

- Japanese patients with T2DM who are prescribed with TRADIANCE® Combination Tablets AP or BP
- Patients who have never been treated with TRADIANCE® Combination Tablets AP or BP before enrolment

Exclusion criteria

None

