9.2.2.3 Patient registration method

The registration method will be a continuous investigation system. Patients who begin treatment with TRADIANCE® Combination Tablets AP or BP after the conclusion of the contract will be registered by entering necessary information in the Electronic Data Capture (EDC) system within 14 days whenever possible from the day of treatment initiation (inclusive).

Patient registration will be stopped when the overall target number of patients for the study is reached. After the end of the registration period, investigators use a signed form to confirm that patients have been registered continuously at the site. A log of all patients included in the study will be maintained at the site.

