9.7.1 Analyses of Safety

[figure not shown]
The safety analysis will include all patients who registered in the study and receiving the TRADIANCE® Combination Tablets AP or BP treatment at least one time except those who are found to have no observation after enrolment, invalid registration, or invalid contract with the site (see section 9.7). In general, safety analyses will be descriptive, based on BI standards, and focus on AEs related to the TRADIANCE® Combination Tablets AP or BP treatment.

Proprietary confidential information © 2018 Boehringer Ingelheim International GmbH or one or more of its affiliated companies

AEs will be coded using the current version of the Medical Dictionary for Drug Regulatory Activities (MedDRA) and will be based on the concept of treatment emergent AEs. To this end, all AEs occurring between the initiation of TRADIANCE® Combination Tablets AP or BP prescribed at baseline visit and 7 days (inclusive) after the last administration will be considered 'treatment emergent'. An AE is considered to be an ADR if either the physician/investigator who has reported the AE or the sponsor assesses its causal relationship as 'related'.

The frequency of ADRs will be tabulated by system organ class and preferred term according to the current MedDRA version. The frequency of SAEs will also be tabulated likewise. The incidence of ADRs stratified based on patient demographics will also be investigated.

No imputation is planned for missing AE data except for missing onset dates which will be handled according to BI standard.

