## **6.7 BASELINE, TIME WINDOWS AND CALCULATED VISITS**

With regard to effectiveness and safety endpoints, the term "baseline" refers to the last observed measurement prior to administration of TRADIANCE®. Observation on the same day as administration of TRADIANCE® is "baseline".

Effectiveness analyses will be performed based on calculated visits as shown in [Table 6.7: 1](#). If two or more data points of a patient fall into the same interval, the closest value to the planned day will be selected. If there are two observations which have the same difference in days to the planned day or if there are two observations on the same day, the first value will be used.

Table 6.7:1 Baseline, time windows and calculated visits

Week label	Planned days	Time window (actual days on treatment)	
		Start	End
Baseline	0	NA	1
Week12	84	2	133
Week26	182	134	231
Week40	280	232	322
Week52/EOT	364	323	End of study

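### SAP exclusion A1.2 is tied to registration, but the protocol registers patients after their first dose, so read literally it removes compliant patients from every analysis

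*SAP*

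**What the plan says.** **The exclusion.** SAP 6.2, Table 6.2:1, row A1.2 reads "Patient received TRADIANCE® treatment before registration". It sits in category A, on entrance criteria. It is detected automatically, excludes from all patient sets, and has nothing in its comment cell. SAP 6.2 states that the table's final column decides which violations remove patients from which set.

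**The registration procedure.** Protocol 9.2.2.3: "Patients who begin treatment with TRADIANCE® Combination Tablets AP or BP after the conclusion of the contract will be registered". The window is 14 days where possible, with the day of initiation counted. Annex 2, footnote *2, says of patients already given the drug that they "will be registered within 14 days from whenever the day of first administration is possible".

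**The safety population.** Protocol 9.7.1 takes "all patients who registered in the study and receiving the TRADIANCE® Combination Tablets AP or BP treatment at least one time", less those with no observation after enrolment, an invalid registration or an invalid site contract. A first dose before registration is not among these exceptions, nor among the three ineligibility criteria in Protocol 9.7.

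**The entry criterion behind A1.2.** Protocol 9.2.2.1: "Patients who have never been treated with TRADIANCE® Combination Tablets AP or BP before enrolment".

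**Declared changes.** SAP 4: "No change has been made in the planned analyses from the statistical methods described in the NIS Protocol".

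**The concern.** The protocol's normal order of events is first dose, then registration. A1.2 treats that order as an entry failure. Because it excludes from all sets, it reaches the safety set and so the primary outcome, the incidence of ADRs.

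If programmed as worded, only patients registered by the day of first dose would remain. Patients registered on that day might also be lost, depending on whether dates or clock times are compared. The analysed group would then be selected by how quickly a site entered its patients, which is not part of the study question. Precision would fall, and the estimate could shift in a direction that nobody can state in advance. The SAP declares no departure from the protocol, so a reader would not know that this had happened.

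**Working it through.** **1. One patient against each rule.** First dose on day 1, registered on day 5, no earlier TRADIANCE.

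| Rule | Result |
|---|---|
| Protocol 9.2.2.3 and Annex 2 *2 (14 days, initiation day counted) | Compliant |
| Protocol 9.2.2.1 (no TRADIANCE before enrolment) | Met if enrolment means starting the study course; not met if it means registration |
| Protocol 9.7 and 9.7.1 (safety analysis) | Included |
| SAP A1.2 as worded | Excluded from all sets |
| SAP G1.3 (registration rule breached) | Does not apply |
| SAP 6.3 (safety set) | Included: registration valid, at least one dose |

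The protocol's entry criterion leaves the date open. A1.2 closes it at registration, which the protocol places after treatment starts. Because the initiation day is counted, day 14 is 13 days after the first dose. The words *whenever possible* allow later registration still.

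**2. The plan's own figure.** Protocol 9.5 claims more than 80% power at n = 1000 to distinguish a hypoglycaemic AE proportion of 2.2% from 1.1% (one-sample chi-square, two-sided 0.05).

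Power = Φ[(|p1 − p0|√n − 1.96√(p0(1−p0))) / √(p1(1−p1))], with p0 = 0.011 and p1 = 0.022.

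- n = 1000: (0.3479 − 0.2044)/0.1467 = 0.978, so power is 83.6%. The claim reproduces (80.8% with continuity correction, 83.4% exact).
- Smallest n for 80%: [(1.96 × 0.1043 + 0.8416 × 0.1467)/0.011]², which rounds up to 889. Losing more than 111 of 1000, about 11%, takes the normal-approximation power below 80%.
- n = 900, 800, 500: power 80.4%, 76.7%, 61.2%.

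This concerns the reference event used for sizing. It is not a test of the primary outcome.

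**3. Precision of the ADR incidence.** Let f be the share registered after the first-dose day and p the ADR incidence. Both are assumptions. The base is the planned safety set of 1000 (Protocol abstract), taken as the set under the intended rule.

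Patients left: n = 1000(1−f). Width factor: 1/√(1−f). Half-width: 1.96√(p(1−p)/n).

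| f | n | Width factor | Half-width, p = 5% | p = 10% | p = 20% |
|---|---|---|---|---|---|
| 0 | 1000 | 1.000 | 1.35 | 1.86 | 2.48 |
| 0.10 | 900 | 1.054 | 1.42 | 1.96 | 2.61 |
| 0.25 | 750 | 1.155 | 1.56 | 2.15 | 2.86 |
| 0.50 | 500 | 1.414 | 1.91 | 2.63 | 3.51 |

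Half-widths are in percentage points.

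**4. Shift in the estimate.** The full-set incidence is (1−f)·p_kept + f·p_dropped. The literal rule reports p_kept. The difference is f × (p_kept − p_dropped). The documents give none of these three quantities, so neither the sign nor the size can be stated.

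**The case against.** **The intent is plain, and the fault starts in the protocol.** A1.2 sits among the entrance criteria and paraphrases the protocol's own inclusion criterion. The protocol itself uses enrolment and registration interchangeably: Protocol 9.7 and 9.7.1 describe the same exclusion, once with each word. Registration breaches and starts outside the registration period have their own rows (G1.3, G1.4). All this points to earlier use as the target. It stands as a reading of intent, and it means the inclusion criterion needs the same clarification. It does not cure the SAP wording: an automated check compares the dates it is given, and A1.2 names registration.

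**SAP 6.3 may keep these patients in.** Its safety set names only invalid registration and absence of a dose, and A1.2 is not in the invalid-registration category (G1). The disagreement is real. However, SAP 6.2 makes the table's final column operative. SAP 6.3 is also not a complete list: its effectiveness set does not mention A1.1 (no type 2 diabetes), which the table excludes from that set. It cannot safely be read as overriding the table.

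**The error would be noticed.** Violations are judged important or not before database lock. The SAP is dated 24 May 2021, well after planned registration ended in January 2020, so registration dates should have been at hand. The analysis data set plan, which is not among the documents, may code the rule as intended. This lowers the practical risk. It remains a hope about later steps, and the meeting's stated task is to judge importance, not to correct a rule.

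**The magnitude is generic.** The width factor describes any loss of patients. That is fair, and the figures above are illustrations only.

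**Conclusion.** The concern holds. As worded, A1.2 conflicts with the registration procedure in Protocol 9.2.2.3 and Annex 2 and with the safety population in Protocol 9.7.1. It would remove patients who did everything the protocol asks. Confidence in the wording conflict is high.

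The effect on this study cannot be determined from the documents. It rests on f, which is unknown, and on how the check was programmed, which is not visible. Nothing shows that a wrong exclusion took place. The study is descriptive and the intent can be inferred, so this is a point that should be fixed and not a fatal one. It deserves correction because the rule helps to define the population for the primary outcome and the remedy is very cheap.

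**What to change.** 1. Reword A1.2 to: *Patient received TRADIANCE® before the first administration date recorded for this study*, and programme it against that date. SAP 6.7 already uses this anchor: baseline "refers to the last observed measurement prior to administration of TRADIANCE".
2. Leave late registration to G1.3.
3. State in SAP 6.2 that, for analysis, enrolment in the protocol's inclusion criterion is read in the same way.
4. In SAP 6.3, refer to the final column of Table 6.2:1, so that the set definitions and the table agree.
5. State the limit of the check. It must draw on the prior-antidiabetic records, which Annex 2, footnote *4, starts 3 months before first administration. Earlier TRADIANCE use may go undetected.
6. If the check has already been run, compare the A1.2 exclusions with the first-dose and registration dates.

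The cost is one table cell, the reference date in one programmed check, and one sentence each in SAP 6.2 (item 3) and SAP 6.3 (item 4), plus a line for the limit in item 5. No new data are needed. The one downside is the 3-month look-back.
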